## **Normality Testing**

Kolmogorov–Smirnov and Shapiro–Wilk tests assessed normality.

## **Comparative Analyses**

- Kruskal–Wallis tests with Dunn–Bonferroni post hoc comparisons for non-normally distributed continuous outcomes.
- One-way ANOVA with Tukey HSD for key binocular outcomes when appropriate.
- Chi-square or Fisher’s exact tests for categorical variables.
- GEE model with exchangeable correlation structure for binocular UIVA to account for within-subject correlation.

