### Primary Outcomes (6 months):

- Binocular UDVA, UIVA, UNVA (logMAR).
- Patient satisfaction scores for distance, intermediate, and near spectacle-free vision (0–10 scale).

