## **Sample Size**

A post hoc power analysis (one-way ANOVA; Cohen's  $f = 0.25$ , alpha 0.05, three groups,  $n = 197$ ) yielded power of 0.96.

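### No primary outcome is tied to one test, and ANOVA/Tukey have no fallback for unequal variances; the size of the variance risk depends on group sizes and SDs that are not given

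*Combined protocol and SAP*

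**What the plan says.** The protocol names six primary outcomes at 6 months: "Binocular UDVA, UIVA, UNVA (logMAR" and "Patient satisfaction scores for distance, intermediate, and near spectacle-free vision", the latter on a 0–10 scale.

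The SAP (Normality Testing) says "Kolmogorov–Smirnov and Shapiro–Wilk tests assessed normality". Comparative Analyses then lists "Kruskal–Wallis tests with Dunn–Bonferroni post hoc comparisons for non-normally distributed continuous outcomes" and, as a separate item, "One-way ANOVA with Tukey HSD for key binocular outcomes when appropriate". A further item assigns a GEE with exchangeable correlation to binocular UIVA, which is itself a primary outcome. Neither section mentions a check of equal variance or a test that does without it.

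The Sample Size section rests on ANOVA alone: "A post hoc power analysis (one-way ANOVA", with "alpha 0.05, three groups", f = 0.25 and n = 197. The design is a retrospective, non-randomised consecutive series, and no size per lens group is stated.

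**The concern.** Three things are left open. The SAP does not define which binocular outcomes are *key*, nor the condition under which ANOVA applies. It gives no cut-off for the normality tests, no rule for when the two disagree, and no statement of whether they are run per group or on residuals. The choice of test can therefore be settled after the results are visible. The candidates also answer different questions: ANOVA compares means, Kruskal-Wallis compares rank distributions and gives no logMAR difference.

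Separately, the plan screens for non-normality, which matters little for means at about 66 patients per group (197/3 = 65.7). It does not guard against unequal variances, which matter when group sizes differ. Three optical designs could plausibly differ in spread, especially at intermediate and near, and nothing in the design makes the groups equal in size. At stake are the primary p-values and what they mean.

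**Working it through.** **Inputs from the documents:** N = 197, three groups, alpha 0.05, f = 0.25, six primary outcomes. **Assumed, because not given:** group sizes, SD ratios, the acuity step and the shape of the satisfaction scores.

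**1. The plan's own figure.** For one-way ANOVA the noncentrality is λ = N·f² = 197 × 0.0625 = 12.31 with df 2 and 194, which gives power 0.887. The plan says its analysis "yielded power of 0.96", so the figure does not reproduce. That is a separate matter. What counts here is that the calculation is for ANOVA with one common SD.

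**2. Which rules apply to which outcome.**

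| Primary outcome | Candidate analyses |
|---|---|
| Binocular UDVA, UNVA | Kruskal-Wallis; ANOVA/Tukey |
| Binocular UIVA | Kruskal-Wallis; ANOVA/Tukey; GEE |
| Three satisfaction scores | Kruskal-Wallis if non-normal; otherwise ANOVA only if they count as key binocular outcomes |

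**3. How often the normality screen would fire.** At n = 66, simulated acuity in 0.1 logMAR steps (SD 0.1) failed Shapiro-Wilk in 1000 of 1000 samples. So did whole-number 0–10 scores (assumed mean 8, SD 1.5). With 0.02 logMAR steps only 6% failed, so for acuity this depends on line scoring, which the documents do not specify. With perfectly normal data, testing each of three groups at 0.05 rejects in at least one group with probability 1 − 0.95³ = 0.143; the simulation gave 13–15%.

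**4. Error from choosing the test, equal SDs.** A mechanical rule (Shapiro-Wilk, then choose) gave 4.5–5.0%. Taking the smaller p-value of ANOVA and Kruskal-Wallis gave 5.3–7.2% over normal, skewed and stepped data, and about 6% with normal data.

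**5. Why unequal variances matter.** ANOVA and Tukey use s²pooled = Σ(nᵢ − 1)sᵢ² / (N − 3). Put in expected values for SDs 1/1/2 and compare the first and third groups:
- 97/60/40: (96 + 59 + 39×4)/194 = 311/194 = 1.603. Pooled SE = √[1.603(1/97 + 1/40)] = 0.238; true SE = √(1/97 + 4/40) = 0.332. The SE is understated (ratio 0.72).
- 40/60/97: (39 + 59 + 96×4)/194 = 482/194 = 2.485. Pooled SE = √[2.485(1/40 + 1/97)] = 0.296; true SE = √(1/40 + 4/97) = 0.257. The SE is overstated (ratio 1.15).

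Simulated type I error at nominal 5% (normal data, null true, 100,000 runs per row):

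| Sizes | SDs | ANOVA | Tukey | Welch | Games-Howell |
|---|---|---|---|---|---|
| 66/66/65 | 1/1.25/1.5 | 5.3% | 5.3% | 5.1% | 5.1% |
| 66/66/65 | 1/1.5/2 | 5.6% | 5.6% | 5.0% | 4.9% |
| 97/60/40 | 1/1.25/1.5 | 8.2% | 8.4% | 4.9% | 4.8% |
| 97/60/40 | 1/1.5/2 | 10.8% | 11.0% | 5.1% | 4.7% |
| 40/60/97 | 1/1.25/1.5 | 3.1% | 3.0% | 5.0% | 5.0% |
| 40/60/97 | 1/1.5/2 | 2.6% | 2.4% | 5.0% | 5.0% |

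With only the third group more variable (1/1/1.5 to 1/1/2), separate smaller runs gave ANOVA 8.7–9.0% to 11.7–12.5% at 97/60/40, and 2.0–2.5% at 40/60/97.

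**6. Limits of Welch.** With identical 0–10 distributions in all groups, 97/60/40 and an assumed 80% of patients at 10, ANOVA gave 4.8%, Kruskal-Wallis 4.9% and Welch 8.2%. A separate run with ceiling-heavy scores and unequal groups gave 4.4%, 4.7% and 7.4%. With 55% at 10 the figures were 5.1%, 5.0% and 6.3%.

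**7. Power cost of Welch when SDs are equal (f = 0.25).** From 0.887 to 0.884 with near-equal groups; from 0.885–0.887 to 0.877–0.882 at 97/60/40.

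**The case against.** The two rules can be read as one sequence: test normality, use Kruskal-Wallis if it fails, and use ANOVA only when its assumptions hold. On that reading, outcomes that always fail the screen always go to Kruskal-Wallis, and with equal SDs a mechanical rule barely disturbs the error rate. This is fair, but the SAP does not say it. The cut-off, the tie-break and the list of key outcomes would still be missing, and UIVA would still have its GEE.

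A reader might infer that the primary tests run at 9–12% error. The documents do not support that: it needs unequal groups and the smallest group to be the most variable, and neither sizes nor SDs are given. The opposite pairing makes ANOVA conservative. Nor do the documents show that anyone chose a test by its p-value; they only leave room for it.

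A reader might also infer that Welch's test should replace everything. Step 6 shows why not: for ceiling-heavy satisfaction scores it can be the worst of the three.

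Two smaller objections also stand. Mean ± SD reporting lets a logMAR difference be derived beside a rank test, so only its confidence interval is missing. And naming a test now is itself a change made after the data exist.

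**Conclusion.** The concern holds in two parts of different strength. That no primary outcome is tied to one analysis follows directly from the text. Its main harm is undefined discretion and a shifting hypothesis; the numerical inflation from choice alone is modest (about 6% with normal data and equal SDs).

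The missing protection against unequal variances is a conditional risk. Under the assumed 97/60/40 and 40/60/97 splits with SD ratios of 1.5 to 2, ANOVA's type I error lies between about 2% and about 12%, according to which group is most variable; with near-equal groups it is about 5–6%. The actual group sizes and SDs would settle where this study falls.

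**What to change.** Stop using normality tests to select the analysis, and name one primary analysis per outcome:

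- **Three binocular acuities:** Welch's ANOVA with Games-Howell pairs (or a linear model with heteroscedasticity-robust SEs), reporting mean logMAR differences with 95% CIs. Kruskal-Wallis/Dunn as sensitivity.
- **Three satisfaction scores:** Kruskal-Wallis with Dunn-Bonferroni as primary, interpreted as a comparison of distributions and not of means. Mean differences with CIs as supportive.
- **GEE for UIVA:** label it a sensitivity analysis. A binocular acuity is normally one value per patient per distance, so state what within-subject correlation the model is meant to handle.
- **Reporting:** give group sizes and SDs, show both the mean-based and the rank-based analysis for all six outcomes, and disclose that the tests were fixed after data collection.

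The cost is revised SAP wording, a re-run, at most about one point of power if variances are equal, and a disclosed late change. This does not deal with multiplicity over six primary outcomes or with confounding in a non-randomised series, which need separate handling.

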## Study Design

Consecutive, comparative, retrospective case series of patients undergoing bilateral phacoemulsification with implantation of the same IOL model in both eyes.

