### Secondary Outcomes (6 months):

- Monocular UDVA, UIVA, UNVA (logMAR).
- Monocular and binocular CDVA, CIVA, CNVA.
- Manifest and objective spherical equivalent refraction.
- Binocular defocus curve performance.

- Halo and glare scores (NEI-RQL-42 items 17 and 38; 0–100 scale).

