# **Statistical Analysis Plan (SAP)**

## **Analysis Population**

All eligible patients completing 6-month follow-up were included. Both eyes contributed to outcomes; inter-eye correlation was addressed using GEE for selected analyses.

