## **Significance Threshold**

Two-tailed  $p \leq 0.05$  considered statistically significant.

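### The only named GEE is assigned to an outcome with one value per patient, while the secondary outcomes measured in both eyes have no named method for inter-eye correlation

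*Combined protocol and SAP*

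**What the plan says.** - **Design.** Study Design describes bilateral surgery with "implantation of the same IOL model in both eyes", so lens group is constant within a patient.
- **Unit of analysis.** SAP, Analysis Population: "Both eyes contributed to outcomes; inter-eye correlation was addressed using GEE for selected analyses".
- **The one named GEE.** SAP, Comparative Analyses: "GEE model with exchangeable correlation structure for binocular UIVA to account for within-subject correlation".
- **Other tests.** The same section gives Kruskal–Wallis with Dunn–Bonferroni to non-normal continuous outcomes, and one-way ANOVA with Tukey HSD to key binocular outcomes. It makes no separate provision for monocular data.
- **Outcomes.** Assessments and Outcome Measures puts intermediate acuity at 66 cm and at the 6-month visit. Primary Outcomes lists binocular UDVA, UIVA and UNVA and the satisfaction scores. Secondary Outcomes includes monocular uncorrected acuities, monocular corrected acuities, and manifest and objective spherical equivalent.
- **Threshold.** Significance Threshold sets a two-sided 0.05 limit.

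**The concern.** The plan recognises that two eyes of one patient are correlated, but the only correction it names is attached to an outcome that does not have that problem. A both-eyes-open acuity at one distance and one visit gives a single number per patient. The outcomes with a left and a right value appear to fall to a rank test that treats every observation as independent.

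Because both eyes carry the same lens, group is a between-patient factor. Positive inter-eye correlation then raises the variance of each group average above what an independence test assumes. Pooling the eyes gives p-values that are too small, and the pairwise post hoc comparisons share the defect. At stake are the between-lens claims on monocular acuity and refraction.

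**Working it through.** **The plan's own figures.** The documents give no type I error for eye-level tests and no inter-eye correlation, so there is nothing to reproduce on this point. The one computed figure is in Sample Size, where the post hoc analysis "yielded power of 0.96". From its stated inputs (f = 0.25, alpha 0.05, three groups, n = 197), a noncentral F with λ = f²N = 0.0625 × 197 = 12.3 and df 2 and 194 gives 0.887, not 0.96. That is a separate matter, and nothing below depends on it.

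**Step 1: values per patient.**

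| Outcome | Values per patient at 6 months | Method named |
|---|---|---|
| Binocular UIVA | 1 | GEE, exchangeable |
| Other binocular acuities, satisfaction | 1 | Kruskal–Wallis; ANOVA for key binocular outcomes |
| Monocular UDVA, UIVA, UNVA | 2 | Kruskal–Wallis if non-normal; no clustered method |
| Monocular CDVA, CIVA, CNVA | 2 | as above |
| Manifest and objective spherical equivalent (eye-level by nature) | 2 | as above |

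For eye-level outcomes that pass the normality tests, no test is named, because ANOVA is limited to key binocular outcomes. With one row per patient, the exchangeable parameter cannot be estimated, and the GEE for binocular UIVA reduces to ordinary regression with robust standard errors.

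**Step 2: effect of pooling eyes.** Inputs: two eyes per patient (Study Design); alpha 0.05 (Significance Threshold); three groups. The inter-eye correlation ρ is an assumption, shown from 0.3 to 0.9.

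Design effect = 1 + (2 − 1)ρ = 1 + ρ. The 2-df statistic is inflated by about this factor, and the 5% critical value of chi-square on 2 df is 5.991, so

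true type I error ≈ P(χ²₂ > 5.991/(1 + ρ)) = exp(−5.991 / (2(1 + ρ))).

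- ρ = 0.3: exp(−5.991/2.6) = 0.100
- ρ = 0.5: exp(−5.991/3.0) = 0.136
- ρ = 0.7: exp(−5.991/3.4) = 0.172
- ρ = 0.9: exp(−5.991/3.8) = 0.207

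**Step 3: simulation check.** There were 10,000 runs per setting, with normal data and near-equal groups (group sizes are not given). Sample Size does not say whether 197 counts patients or eyes, so both cases were run. Entries are rejection rates of Kruskal–Wallis on pooled eyes under a true null.

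| ρ | 197 patients, 394 eyes | 98 patients, 196 eyes |
|---|---|---|
| 0 | 0.047 | 0.050 |
| 0.3 | 0.097 | 0.096 |
| 0.5 | 0.135 | 0.125 |
| 0.7 | 0.166 | 0.167 |
| 0.9 | 0.200 | 0.211 |

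The inflation is much the same whichever unit 197 counts.

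**Step 4: after correction.** With 197 patients, Kruskal–Wallis on the patient mean rejects 4.6% to 5.0% of the time, and a cluster-robust Wald test equivalent to the GEE 5.3% to 5.7%. With 98 patients the figures are 4.6% to 5.0% and 6.2% to 6.4%; the robust test is slightly liberal in the smaller sample.

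**Step 5: information content.** If 197 counts patients, 394 eyes are worth 394/(1 + ρ) independent eyes: 303, 263, 232 and 207 at ρ = 0.3, 0.5, 0.7 and 0.9.

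**The case against.** **The list of GEE analyses may be incomplete.** Analysis Population speaks of selected analyses in the plural, while Comparative Analyses names one. *Binocular* could also be a slip for *monocular*. Neither reading settles the matter. No monocular outcome is named for GEE anywhere, and if the slip is assumed, the other monocular acuities and refraction are still uncovered. What stands is that the plan does not say how monocular values enter each test, so the inflation is conditional on both eyes being pooled. The statement that both eyes contributed points that way, and nothing mentions one eye or the patient mean.

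**The harm is limited.** This stands in full. The affected outcomes are secondary, and a GEE with cluster size 1 is redundant rather than harmful.

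**The size rests on an assumed correlation.** This also stands, which is why a range is shown. Even at ρ = 0.3 the nominal error roughly doubles.

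**Stronger readings that a reader might infer.**

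- A within-subject model for binocular UIVA might suggest a file with two rows per patient, so that the primary outcomes are counted twice. At ρ = 1 the formula would give exp(−5.991/4) = 0.224. No section describes the data layout, and a needless GEE on one row per patient explains the wording equally well.
- One might say that ANOVA is run on pooled eyes. Comparative Analyses reserves ANOVA for key binocular outcomes.
- One might add that confidence intervals are too narrow. The plan specifies none; it gives means with SDs, tests and a p-value threshold.

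**Conclusion.** The plan is wrong as written on this point. Its only named correction for clustering goes to an outcome with no clustering, and the outcomes with two eyes per patient are left without one.

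If both eyes are pooled in Kruskal–Wallis, a nominal 5% three-group comparison has a true type I error of about 10% to 21%. By the same approximation, a nominal p of 0.01 corresponds to about 0.03 to 0.09. These figures assume an inter-eye correlation between 0.3 and 0.9, which the documents do not give. The simulations behind them also assume normal data and near-equal groups.

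The mismatch in the text is certain, whereas the realised inflation depends on pooling and on a positive correlation. It reaches only the secondary eye-level acuities and refraction. It should not be read as showing that the primary p-values are inflated, because each primary outcome has one value per patient.

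**What to change.** 1. Analyse binocular and questionnaire outcomes with one row per patient and no GEE. For the defocus curve this means one value per patient at each defocus level.
2. Analyse every eye-level acuity and refraction outcome by one stated method that respects the pairing:
   - a GEE with patient as cluster, exchangeable correlation and robust standard errors;
   - a mixed model with a patient random intercept; or
   - Kruskal–Wallis on the patient mean or on one pre-specified eye.
3. State the analysis unit for each outcome, and whether n = 197 counts patients or eyes.

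The cost is a change of SAP wording and a re-run of the eye-level analyses on data already held. The p-values for the eye-level secondary outcomes will be larger, and some nominally significant differences may not survive. With far fewer than 197 patients, the uncorrected robust test is slightly liberal (Step 4), which favours the patient-mean option.

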## **Significance Threshold**

Two-tailed  $p \leq 0.05$  considered statistically significant.

## **Software**

IBM SPSS Statistics version 24.0 (IBM Corp., Armonk, NY, USA).
